To induce elevations in blood lactate, an incremental load test will be applied on a stationary bicycle, in which the pedaling load will be increased every 3 minutes (30W; maintaining a pedaling speed of 60-70 revolutions per minute) until reaching the point of fatigue. Before starting the test, resting variables such as heart rate, subjective sensation of effort (SSE), blood pressure, pulse oximetry and muscle (vastus lateralis of quadriceps) will be recorded. In addition, a venous blood sample will be taken in a 2 ml tube with EDTA and another tube without anticoagulant for the subsequent plasma measurement of FGF21 and complementary biochemical tests (glycemia, insulin, lipid profile, transaminases and renal function markers), in addition to the measurement of lactate from a finger prick with a sterile lancet. In addition, urine samples will be taken both before and after exercise to measure renal function markers (proteinuria, creatinuria, albuminuria, glucosuria).

SPSS version 22 and GraphPad Prism version 8 software for Windows will be used. Quantitative variables will be described in terms of median and interquartile range and qualitative variables in terms of absolute frequencies. To make comparisons before and after the training program, the Wilcoxon test or Student t test for related samples will be used, depending on the distribution of the variables. To investigate the presence of correlations between the variables of interest, the Spearman coefficient will be used. The sample size calculation was carried out considering the following parameters: a power of 95%, an alpha value of 0.05, a difference in pre- and post-

intervention means of 50 (100 vs 150) pg/ml, with a standard deviation for both groups of 50 pg/ml. With these data, the sample size is 16 participants, and considering a 20% drop-off, the final size is 20 participants. A p value < 0.05 will be considered statistically significant for all analyses.

Expected results: It is expected to observe that the variations in blood lactate induced by exercise will be associated with changes in plasma concentrations of FGF21, in order to postulate lactate as one of the factors that modulate the production of this factor, and that, therefore, it could play a relevant role in the normalization of the metabolic function associated with exercise.

BACKGROUND

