Considering the above, lactate has recently been proposed as a potential mediator of FGF21 release. Thus, Jeanson et al. described rapid elevations of FGF21 from mouse adipocytes after treatment with increasing concentrations of lactate, where the authors hypothesized that these elevations of FGF21 could have both autocrine and endocrine characteristics (17). In addition, similar results were described by Villarroya et al. in myotubes, in which increasing concentrations of lactate correspondingly and autocrinely increased the concentrations of FGF21, both in terms of messenger RNA and protein (18). The authors detail that the lactate concentrations necessary to produce these effects are in the order of >3 mM, concentrations that can be physiologically found in the circulation during physical exercise, particularly at moderate to high intensities (19). In addition, it has been described that blood lactate is also related to markers of function of other organs of high metabolic relevance, such as the kidney and liver. Thus, in people with type 2 diabetes mellitus (DM2), serum lactate levels were independently and positively related to alanine aminotransferase (GPT) levels (20), so it would be interesting to observe whether high-intensity physical efforts, which generate significant elevations of lactate, influence these markers of liver damage. From a renal point of view, similar results were found in a similar sample of more than a thousand people with DM2 in which, even in the absence of renal dysfunction, positive relationships were observed between blood lactate and creatinine, urea nitrogen, as well as with the transaminase GPT (21). Therefore, it would be relevant to observe whether high-intensity physical efforts have an impact on these markers of renal function acutely (after a session) in order to manage safety parameters when implementing these intervention strategies in physically inactive people.

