Taken together, these findings suggest that lactate would play a relevant role in the regulation of circulating concentrations of FGF21, as well as markers of tissue stress in the kidney and liver. However, the evidence in this regard is based mainly on findings in cell cultures or observational clinical studies, highlighting the absence of quasi-experimental or experimental clinical studies focused on solving this problem, in order to explore the potential relationships between transient elevations of circulating lactate during exercise with those of other metabolic mediators such as FGF21 and tissue function markers (e.g. liver and kidney) (Figure 2). Therefore, and taking advantage of the widely described elevations of lactate concentrations after high-intensity exercise and/or close to fatigue levels (14), the present study aims to investigate the influence of variations in lactate concentrations on circulating FGF21 after incremental physical exercise until fatigue, in a clinical context.

Working hypothesis

The expected increase in blood lactate following incremental exercise to fatigue will increase plasma levels of FGF21 in physically inactive adults.

General aim

To investigate the influence of exercise-influenced changes in blood lactate on plasma concentration of FGF21 in physically inactive individuals.

Specific aims

- To characterize the phenotype of the study sample.
- To compare blood lactate levels pre and post incremental exercise.
- To compare plasma FGF21 levels pre and post incremental exercise.
- To relate changes in blood lactate to changes in plasma FGF21 pre and post incremental exercise.

Secondary aims

- To compare blood levels of kidney function markers in blood (creatinine, urea nitrogen, urea acid and urea) and urine pre and post incremental exercise.
- To compare blood levels of transaminases (GPT and GOT) pre and post incremental exercise.
- To relate changes in blood lactate to changes in renal function markers and blood transaminases pre and post incremental exercise.

METHODOLOGY

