Design: This is a quasi-experimental study comparing pre- and post-intervention. The research question is associated with investigating the influence of changes in blood lactate influenced by exercise on the plasma concentration of FGF21 in physically inactive people. This project has the approval of the Scientific Ethics Committee of the Valdivia Health Service (Ord. 222/2022) and has Biosafety certification by the Institutional Biosafety Committee of the Austral University of Chile (No. 36/23).

Sample: People over 18 years of age (and up to 30 years of age) enrolled in the Kinesiology program at the Austral University of Chile will be included. They must be physically inactive (perform less than 150 minutes/week of moderate physical activity and/or 75 minutes/week of vigorous physical activity) and without medical contraindications to perform physical activity. People who are taking medications that influence blood glucose or insulin levels and/or with anti-inflammatory effects will be excluded. The sample size calculation was performed considering the following parameters: a power of 95%, an alpha value of 0.05, a difference in pre- and post-intervention means of FGF21 of 50 pg/ml (100 vs 150 pg/ml), with a standard deviation for both groups of 50 pg/ml (according to the studies by Sabaratnam et al. and Slusher et al.: references 10 and 11 of point 3.1). With these data, the sample size is 16 participants, and considering a 20% drop-off, the final size is 20 participants, where recruitment will be by convenience and maintaining gender parity.

Variables: At the time of entering the study, the age in years and sex of the participants will be recorded. Anthropometric variables such as weight in kilograms and height in meters will be

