recorded using a scale (InBody® 270) and a height rod (SECA) respectively. From these measurements, the body mass index (BMI) will be calculated in kilograms/meters². For the calculations of the waist-hip ratio (WHR) and waist-height ratio (WHR), the waist circumference will be measured in centimetres using the navel area as a reference point. The hip circumference will be measured as the largest circumference obtained at the trochanteric femoral level. The levels of total and segmental muscle and fat mass will be measured using the InBody® 270 bioimpedance meter. The level of spontaneous physical activity will be measured using the International Physical Activity Questionnaire (IPAQ) in its short version. To induce elevations in blood lactate, an incremental load test will be applied on a cycle ergometer or stationary bicycle, in which the pedalling load will be increased by 30W every 3 minutes, starting from an initial load of 30W until reaching the point of fatigue. Before starting the test, participants will remain seated for 10 minutes, during which time heart rate, subjective sense of exertion (SSE) with the modified Borg Scale, blood pressure, pulse oximetry and muscle (vastus lateralis of quadriceps) will be recorded at rest. In addition, a venous blood sample will be taken in a 2 ml tube with EDTA and another tube without anticoagulant for the subsequent plasma measurement of FGF21 with a specific ELISA kit for this (RayBio® catalog ELH-FGF21) and complementary biochemical tests (glycemia, insulinemia, total cholesterol, triglycerides, HDL, LDL, VLDL, non-HDL cholesterol, transaminases (GOT and GPT), creatinine, uric acid, urea and urea nitrogen). In addition, lactate measurement will be performed from a digital prick with a sterile lancet. For this, a specific reactive strip will be used, which will be measured with the AccuTrend Plus® device. In parallel, the participant will be asked to bring a urine sample from the same day on an empty stomach for biochemical analysis (proteinuria, creatinine clearance, albuminuria, glucosuria). Once these measurements have been taken at rest, the incremental stress test will begin. Thus, on a cycle ergometer each participant will begin the test with a pedalling cadence of 60-70 RPM at 30W load. Every 3 minutes this load will increase by 30W, always maintaining the same pedalling cadence. During the execution of the test, participants will always be supervised and guided by a professional kinesiologist. Heart rate, pulse and muscle oximetry, and SSE will be assessed minute by minute, while blood pressure will be measured every 3 minutes. At the end of the test, the test execution time, the distance travelled in meters, heart rate, blood pressure, SSE and final pulse and muscle oximetry will be recorded. The percentage of frequency reserve used during the test will be calculated with the Karvonen formula, which depends on the heart rates at rest and post-test. Fatigue at the end of the test will be understood as or the fulfillment of one or more of the following criteria: use of heart rate reserve $\geq 90\%$, subjective feeling of effort $\geq 18/20$ according to the original Borg scale, blood pressure $\geq 200/100$ mg of Hg, desire of the participant to finish the test (Figure 3).

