
Immediately after the test, a new venous blood sample will be taken in a 2 ml EDTA tube and in another tube without anticoagulant. In addition, the post-exercise blood lactate concentration will be measured by finger prick using a specific reagent strip and with the AccuTrend Plus® device. In addition, a post-exercise urine sample will be requested for biochemical analysis previously described. Subsequently, the participant's vital signs will be monitored for 10 minutes after the test to ensure proper recovery.

It is reiterated that, as an assessment of potential confounding/intermediate variables, the following biochemical parameters will be measured from blood samples taken pre- and post-exercise: Total cholesterol, triglycerides, HDL, LDL, VLDL, non-HDL cholesterol, insulin, glucose and transaminases

(GOT, GPT), creatinine, uric acid, urea and urea nitrogen. While, for urine samples, the levels of proteinuria, albuminuria, creatinine clearance, and glucosuria will be assessed.

Statistical analysis

Quantitative variables will be expressed as median and interquartile range, while qualitative variables will be described in terms of absolute frequencies. To calculate potential differences between pre- and post-stress test values, particularly lactate and FGF21, as well as transaminase levels and kidney function markers, the Wilcoxon test or Student t test for related samples will be used, depending on how the data distribution behaves (normal or nonparametric). In addition, associations between lactate and FGF21 concentrations, both pre- and post-exercise, will be explored using the Spearman correlation index and bivariate regression models. In addition, other potential associations of interest will be explored using the Spearman correlation index. For all analyses, a p value equal to or less than 0.05 will be considered statistically significant, using SPSS version 20 and GraphPad version 8 software.

References

1. OMS. Physical Inactivity 2022 [Available from: <https://www.who.int/data/gho/indicator-metadata-registry/imr-details/3416>.
3. Pedersen BK. The diseasesome of physical inactivity - and the role of myokines in muscle-fat cross talk. *The Journal of Physiology*. 2009;587(23):5559-68.

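### The urine panel names creatinuria in one list and creatinine clearance in two, and the collections described do not supply the volume and interval that a measured clearance needs

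*Protocol*

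**What the plan says.** The abstract says that "urine samples will be taken both before and after exercise to measure renal function markers (proteinuria, creatinuria, albuminuria, glucosuria"). In the Methodology, under Variables, the participant is asked to "bring a urine sample from the same day on an empty stomach for biochemical analysis (proteinuria, creatinine clearance, albuminuria, glucosuria"). For the second time point, "a post-exercise urine sample will be requested for biochemical analysis previously described". The same section then restates the panel: "for urine samples, the levels of proteinuria, albuminuria, creatinine clearance, and glucosuria will be assessed".

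The urine markers serve a stated objective. The first secondary aim is "To compare blood levels of kidney function markers in blood (creatinine, urea nitrogen, urea acid and urea) and urine pre and post incremental exercise", and the third relates the change in lactate to the change in renal markers. The Statistical analysis section assigns kidney function markers a paired Wilcoxon or t test. The Background gives the reason: "it would be relevant to observe whether high-intensity physical efforts have an impact on these markers of renal function acutely (after a session").

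**The concern.** Urinary creatinine is a measurement on a single specimen. Creatinine clearance is a volume of blood cleared per unit of time, built from a urine value, a blood value and a urine flow. A laboratory or analyst working from the abstract would report one variable, and one working from the Methodology would report another.

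The version in the Methodology is also the harder one to deliver, because the specimens it describes come without the flow term. What is at stake is whether one of the four urine markers in the secondary aims can be produced, and whether the albumin and protein results will be expressed in a way that is robust to how concentrated each specimen happens to be.

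**Working it through.** The protocol gives no figure to reproduce, so the check compares texts and then works through the algebra.

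**Step 1: the three lists.**
- Abstract: proteinuria, albuminuria, glucosuria, and *creatinuria*.
- Methodology, resting sample: proteinuria, albuminuria, glucosuria, and *creatinine clearance*.
- Methodology, restated panel: proteinuria, albuminuria, glucosuria, and *creatinine clearance*.

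Three of four items agree throughout. The fourth conflicts, one list against two.

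**Step 2: what a measured clearance needs.** C = (U × V) / (t × P), with U urinary creatinine, V urine volume, t collection interval and P blood creatinine.
- P: available, as blood creatinine is measured before and after exercise.
- U: named in the abstract, and implied by any clearance that is measured in urine.
- V: not described for either sample.
- t: not described for either sample.

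The protocol does record one duration: "At the end of the test, the test execution time, the distance travelled in meters, heart rate, blood pressure, SSE" are noted. Test duration is not a urine collection interval. The resting specimen is brought in by the participant, and no bladder emptying just before the test is described, so urine passed afterwards cannot be assigned to the exercise period.

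**Step 3: does the missing flow matter?** C is proportional to V/t. With U and P fixed, doubling V/t doubles C. As an illustration with assumed values that are not in the protocol, take U = 100 mg/dL and P = 0.9 mg/dL, so U/P = 111:
- V/t = 0.5 mL/min gives C = 111 × 0.5 ≈ 56 mL/min
- V/t = 1.0 mL/min gives C ≈ 111 mL/min
- V/t = 2.0 mL/min gives C ≈ 222 mL/min

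The same pair of creatinine values fits a fourfold range, so clearance is not identified without the flow.

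**Step 4: could it be an estimate by formula?** Such an estimate has the form f(age, sex, weight, P). The protocol says "At the time of entering the study, the age in years and sex of the participants will be recorded"; weight is taken with the entry anthropometry and no repeat weighing is described. The pre/post contrast is then f(age, sex, weight, P_post) against f(age, sex, weight, P_pre), which moves only through P. No formula is named, and the result would be a blood measure listed under urine.

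**Step 5: why urinary creatinine is the useful item.** If urine is concentrated by a factor k, albumin A becomes kA and creatinine U becomes kU. The level A changes k-fold, while A/U = kA/kU is unchanged. With k = 2, the unindexed level doubles and the ratio does not move. The same holds for protein. The factor 2 only shows proportionality; it is not a forecast for this trial.

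**The case against.** The strongest defence is that this is loose wording. The document has similar slips: the first secondary aim lists urea acid among the blood markers where the Methodology has uric acid. No aim names clearance, and the Methodology introduces the biochemistry as a check on confounding or intermediate variables. This supports a low severity. It does not remove the conflict, because the clearance wording stands twice in the operative section and the secondary aims do compare urine markers before and after exercise.

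A second objection is that the protocol never calls the samples spot or untimed, so the missing volume and interval are inferred from silence. That is fair. The conclusion is limited to the collections as described: a sample that is brought, and a sample that is requested.

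A third is that such detail belongs in an analysis plan or laboratory manual. How a marker is expressed may well belong there. A volume that was never recorded cannot be supplied there.

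Two stronger readings are tempting and are not supported. A reader might infer that the Methodology lists leave no urinary creatinine at all, so that albumin and protein could not be indexed. But a measured clearance itself requires a urinary creatinine assay, and the abstract names that marker outright; only its reporting is unclear. A reader might also infer that unindexed albumin and protein concentrations will be compared. The protocol gives no unit for either, so it does not say so.

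**Conclusion.** The point holds and is minor. The three urine lists disagree on one of four items, and a pre/post creatinine clearance is not obtainable from the collections as described. This rests on reading the urine as one specimen per time point with no volume or interval recorded, which is what the text describes but does not state in so many words.

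The effect is confined to the urine part of the secondary aims: the pre/post comparison of urine markers and their relation to lactate change. The lactate and FGF21 aims, the transaminases, the blood renal markers and the sample size do not depend on it. No size of bias is claimed.

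**What to change.** Reconcile the three lists. The simplest way is to replace creatinine clearance with urinary creatinine in both Methodology lists, so that they match the abstract. State that albumin/creatinine and protein/creatinine ratios will be used for the pre/post comparison and for the correlation with lactate change, so that urine concentration alone does not drive the result. A small downside to acknowledge is that the ratios also reflect acute changes in creatinine excretion.

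If clearance is really intended, describe timed collections with recorded volume at both time points and give the formula.

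The first route costs two wording changes and a division. If urinary creatinine is assayed as the abstract says, no new test is needed; otherwise it is one assay per sample, 20 participants × 2 = 40. The second route means recording volume and time for every collection. These cannot be reconstructed later, so the choice should be made before samples are taken.

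### The fourth specific aim relates changes in lactate to changes in FGF21, but the analysis section names only correlations of concentrations

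*Protocol*

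**What the plan says.** The fourth item under Specific aims is "To relate changes in blood lactate to changes in plasma FGF21 pre and post incremental exercise". The Abstract's Expected results are also about changes: "variations in blood lactate induced by exercise will be associated with changes in plasma concentrations of FGF21". The third item under Secondary aims uses the same form for other markers: "To relate changes in blood lactate to changes in renal function markers and blood transaminases pre and post incremental exercise". The General aim is looser and speaks of "exercise-influenced changes in blood lactate on plasma concentration of FGF21", so it could be read either way.

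Methodology, Statistical analysis, names one analysis linking lactate and FGF21: "associations between lactate and FGF21 concentrations, both pre- and post-exercise, will be explored using the Spearman correlation index and bivariate regression models". It then adds that "other potential associations of interest will be explored using the Spearman correlation index". The Abstract's Methodology is equally general: "To investigate the presence of correlations between the variables of interest, the Spearman coefficient will be used".

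The document nowhere defines a post-minus-pre score, a correlation of two changes, or a model of FGF21 adjusted for its baseline. The paired Wilcoxon or t tests take each marker separately and do not relate one change to the other.

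**The concern.** The aim concerns whether people whose lactate rises more also show a larger rise in FGF21. The named analysis asks whether people with higher lactate have higher FGF21 at rest, and again after exercise. A person with high FGF21 throughout adds to the second association but not to the first.

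The Abstract intends to use this association to put lactate forward as a factor that modulates FGF21 production, so it carries the study's central inference. Following the text as written could leave the aim unanswered. The general Spearman sentences also leave room to compute both kinds of correlation and report the more favourable one.

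**Working it through.** **The plan's own figure.** Inputs from Methodology, Sample: FGF21 mean 100 pre and 150 post, "with a standard deviation for both groups of 50 pg/ml", power 95%, alpha 0.05. With SD of change = 50·√(2(1 − r)), where r is the FGF21 pre/post correlation, r = 0.5 gives SD 50 and a standardised effect of 1.0. A two-sided paired t test then has 94.9% power at n = 15 and 96.2% at n = 16, so n = 16; 16/(1 − 0.20) = 20. The figure reproduces at r = 0.5, a value not stated. It concerns the mean FGF21 shift, not the association.

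**Why levels do not determine changes.** For lactate L and FGF21 F:

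cov(ΔL, ΔF) = cov(L_post, F_post) + cov(L_pre, F_pre) − cov(L_post, F_pre) − cov(L_pre, F_post).

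Same-time correlations supply only the first two terms. Assume same-time correlations of 0.3 at both times, equal SDs, pre/post correlation 0.5 for each variable, and a common cross-time correlation c. Each change then has variance 2(1 − 0.5) = 1, and the change correlation is 0.3 + 0.3 − 2c. It equals +0.6, 0.0 or −0.4 for c = 0, 0.3 or 0.5.

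**A form closer to this trial.** If resting lactate varies little, post-exercise lactate behaves like the rise. Let s be the correlation of post FGF21 with the rise and q that of resting FGF21 with the rise. Then

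change correlation = (s − q)/√(2(1 − r)).

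At s = 0.3 and r = 0.5 the denominator is 1, so q = −0.3, 0 or +0.3 gives 0.6, 0.3 or 0.0.

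**Simulation** (20,000 trials per scenario, two-sided p ≤ 0.05). FGF21 means and SDs are the plan's. Assumed: resting lactate 1.5 (SD 0.4) mmol/l, rise 8.5 (SD 2.5) mmol/l, r from 0.2 to 0.9, q from 0 to 0.5.

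*Scenario A: true change correlation 0.6, q = 0.* The implied s is 0.6·√(2(1 − r)).

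| r | SD of FGF21 change | s | Post-level power, n = 20 | Post-level power, n = 16 |
|---|---|---|---|---|
| 0.2 | 63.2 | 0.76 | 96% | 91% |
| 0.3 | 59.2 | 0.71 | 91% | 84% |
| 0.4 | 54.8 | 0.66 | 85% | 75% |
| 0.5 | 50.0 | 0.60 | 75% | 63% |
| 0.6 | 44.7 | 0.54 | 63% | 52% |
| 0.7 | 38.7 | 0.46 | 49% | 39% |
| 0.8 | 31.6 | 0.38 | 33% | 27% |
| 0.9 | 22.4 | 0.27 | 18% | 15% |

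The change–change Spearman test has 76–77% power at n = 20 and about 65% at n = 16 throughout. The level test is therefore stronger below r = 0.5, about equal at 0.5, and much weaker above.

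*Scenario B: no relation between changes, so s = q.*

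| q | Post-level significant, n = 20 | Post-level significant, n = 16 |
|---|---|---|
| 0 | 5% | 5% |
| 0.1 | 7% | 6% |
| 0.2 | 12% | 10% |
| 0.3 | 22% | 18% |
| 0.4 | 37% | 29% |
| 0.5 | 56% | 45% |

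At n = 20 the change–change test stays at about 5%. With q = 0 every test is near 5% under the null.

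**The case against.** The strongest reply is that the text already allows the right analysis. The aim itself uses pre and post to describe changes, so the same words in the analysis section may be loose shorthand. The general Spearman sentences cover any association of interest, and the aims list what is of interest. How a change is scored is also the kind of detail often left to an analysis plan.

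Part of this stands. The wording can be read generously, and the general sentences do permit a change analysis. For the renal and transaminase aim no competing quantity is named, so that aim is merely unspecified rather than contradicted. For lactate and FGF21, however, the section does specify an analysis, and it says concentrations where the aim says changes. The document is also titled as both protocol and statistical analysis plan. Permission is not commitment.

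A second reply is that harm is not shown at the plan's own figures. This also stands as far as it goes. At r = 0.5 scenario A shows no material loss, and scenario B needs a link between resting FGF21 and the lactate rise that the document neither states nor suggests. The simulation shows that the two analyses can disagree in either direction, not that they will.

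Third, change–change is not the best performer everywhere, as the costs given with the fix show. The reason to name it is that it is what the aim asks for.

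**Conclusion.** The concern holds for the fourth specific aim and the expected result, and less clearly for the general aim. The mismatch rests on the text and the covariance identity, not on the simulation. Its numerical size cannot be fixed from the document, because it depends on the FGF21 pre/post correlation and on how resting FGF21 relates to the lactate rise. Over the assumed ranges, at n = 20, the effect of using the post-level test runs from a gain in power (96% against about 77%) to a large loss (18% against about 77%). With no relation between the changes, that test is significant in 5% to 56% of trials. The comparisons of lactate and FGF21 before and after exercise, and the sample size for the FGF21 rise, are untouched. This should be fixed before the data are analysed.

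**What to change.** In Methodology, Statistical analysis, state that the fourth specific aim is analysed by the Spearman correlation of post-minus-pre lactate with post-minus-pre FGF21, and that the pre- and post-exercise level correlations are descriptive. A linear model of post-exercise FGF21 on lactate change, adjusted for pre-exercise FGF21, may be added as a supporting analysis. No rule that the two must agree is needed. The same sentence could cover the third secondary aim.

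The cost is one sentence, since every variable is already collected. The statistical costs are:

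- Change scores carry assay error from two measurements.
- If FGF21 after exercise is linked to lactate only through its baseline, regression to the mean gives a spurious negative correlation. At r = 0.5 and n = 20 the change–change test is significant in 9/13/17% of trials (mean rho −0.14/−0.18/−0.23) for q = 0.3/0.4/0.5, against 5% for the adjusted model.
- Under scenario A at n = 20, change–change (about 77%) has less power than the adjusted model (94/89/87/84% at r = 0.5/0.7/0.8/0.9) and, below r = 0.5, less than the post-level test.
- The adjusted model has its own weakness: under scenario B at r = 0.5 it is significant in 12/18/29% of trials for q = 0.3/0.4/0.5.
- Each analysis remains a between-person association that effort or exercise duration can confound. None establishes by itself that lactate is the cause.

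### Specific aim 4 relates changes in lactate and FGF21, but the analysis relates concentrations at each time point, without resting FGF21 and with no main test among four

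*Protocol*

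**What the plan says.** The General aim is "To investigate the influence of exercise-influenced changes in blood lactate on plasma concentration of FGF21 in physically inactive individuals". The fourth item under Specific aims makes this operational: "To relate changes in blood lactate to changes in plasma FGF21 pre and post incremental exercise". Both concern changes.

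The Statistical analysis section says that "associations between lactate and FGF21 concentrations, both pre- and post-exercise, will be explored using the Spearman correlation index and bivariate regression models". It adds that "other potential associations of interest will be explored using the Spearman correlation index", and sets one threshold: "For all analyses, a p value equal to or less than 0.05 will be considered statistically significant". The Abstract mentions only Spearman for correlations.

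FGF21 is measured in every participant before and immediately after the test (Variables). The sample size rests on the paired FGF21 comparison, not on the association.

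**The concern.** The stated analysis does not carry out the stated aim, in three respects.

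- **Quantity.** The aim concerns change against change; the analysis concerns level against level. A correlation between resting lactate and resting FGF21 involves no exercise, so it cannot bear on an exercise-induced change. Under the common threshold it would still count as a significant lactate-FGF21 association.
- **Baseline.** A bivariate regression has two variables, so resting FGF21 has no place in it. The post-exercise association then mixes each person's habitual FGF21 level with the response, although the habitual level is known for everyone.
- **Deciding test.** Two methods at two time points give four results, with no ranking.

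At stake is how the association result will be read. The Abstract expects it to support lactate as a factor that modulates FGF21, on 16 to 20 people. This is not detail left to a later document: the section states the analysis affirmatively.

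**Working it through.** **1. The plan's own figure, and the correlation it implies.** Inputs (Methodology, Sample): "a power of 95%, an alpha value of 0.05, a difference in pre- and post-intervention means of FGF21 of 50 pg/ml", "with a standard deviation for both groups of 50 pg/ml". With pre-post correlation r, the SD of the paired difference is 50 × √(2(1 − r)). At r = 0.5 this is 50, so the standardised difference is 50/50 = 1. The exact two-sided paired t test then has power 0.949 at n = 15 and 0.962 at n = 16, so n = 16. Dropout: 16/(1 − 0.20) = 20. This matches the plan: "With these data, the sample size is 16 participants, and considering a 20% drop-off, the final size is 20 participants". At r = 0 the same calculation gives 28. So r = 0.5 is implied by N = 16 but is not stated, and two-sided testing is assumed.

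**2. Aim and analysis side by side.**

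| | Specific aim 4 | Statistical analysis |
|---|---|---|
| Lactate | change | concentration, pre and post |
| FGF21 | change | concentration, pre and post |
| Resting FGF21 used | yes, within the change | no |
| Main test | not applicable | none named among 2 methods × 2 times = 4 |

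**3. False-positive rate of the four tests.** Four independent tests would give 1 − 0.95⁴ = 18.5%. These are not independent, because Spearman and the regression slope at one time point largely repeat each other. Simulation with no true association, at n = 16 and n = 20, FGF21 pre-post correlation 0.5 and lactate pre-post correlation 0.3:

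| Data | Any of four | Post-exercise pair |
|---|---|---|
| Normal | 13% | 7% |
| FGF21 log-normal with the plan's ratio of SD to mean, 50/100 | 14% | 7% |
| FGF21 log-normal, log-SD 0.8 | 15% | 8% |
| As above, lactate also log-normal, log-SD 0.5 | 16% | 8% |

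With both variables at log-SD 0.8 the four tests reach 16.3 to 16.7% and the pair just under 9%. If both variables are very stable over time (correlations 0.9 and 0.8), the four-test rate falls to about 11% with normal data and 13% with skewed FGF21.

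**4. Power with and without resting FGF21.** Work in units of the baseline SD. Let post = r × pre + 0.5 × lactate + error, with the lactate measure standardised and independent of resting FGF21. The same lactate measure enters all three analyses, so only the handling of FGF21 differs.

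*Version A: error variance 1 − r².* The post-exercise variance is 1 + 0.25 = 1.25, an SD of 50 × √1.25 = 55.9 pg/ml. At r = 0.5 the correlations with lactate are:
- post-only: 0.5/√1.25 = 0.447
- change score: 0.5/√(2(1 − 0.5) + 0.25) = 0.447
- baseline-adjusted: 0.5/√(0.75 + 0.25) = 0.500

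*Version B: post-exercise SD held at 50, so error variance 1 − r² − 0.25.* At r = 0.5 the correlations are 0.500, 0.500 and 0.5/√0.75 = 0.577.

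Simulated power, post-only / change score / adjusted:

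| r | Version A, n = 16 | Version A, n = 20 | Version B, n = 16 |
|---|---|---|---|
| 0.3 | 43 / 33 / 44% | 53 / 41 / 54% | 53 / 39 / 55% |
| 0.5 | 43 / 43 / 50% | 53 / 53 / 62% | 53 / 53 / 66% |
| 0.7 | 43 / 62 / 65% | 53 / 73 / 77% | 53 / 82 / 88% |

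In version A at n = 16, post-only has a slight edge at r = 0 (43% against 40% adjusted), and at r = 0.9 the change score and adjustment tie (95% and 94%).

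*Cross-check.* Suppose instead that lactate correlates 0.6 with the baseline-adjusted response. At r = 0.5 the post-only and change-score correlations are both 0.6 × √0.75 = 0.520. By Fisher's z at n = 16, power is Φ(0.576 × √13 − 1.96) = 55% for each, against Φ(0.693 × √12 − 1.96) = 67% for adjustment. At r = 0.8 the three are 27%, 64% and 67%.

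**5. Share of post-exercise variance due to baseline.** With SD 50 at both times this is r²: 25% at 0.5, 49% at 0.7, 64% at 0.8.

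**The case against.** - **The protocol already uses resting FGF21.** True of Specific aim 4, since a change contains it, so one cannot say that the protocol as a whole ignores baseline. The analysis section does not follow the aim, and that mismatch is the point. The change-on-change analysis might be placed among the other Spearman associations, but it is not named there. Adding it by both methods makes six tests, with a 17-19% false-positive rate for normal data and 19-21% for skewed FGF21.
- **The associations are only explored.** This softens the error-rate point and stands to that extent. The 0.05 rule nevertheless covers all analyses, and the Abstract expects a conclusion from the association.
- **The association is not all that bears on the hypothesis.** Correct. The Working hypothesis is also addressed by the paired lactate and FGF21 comparisons, so a reader should not infer that the general aim rests on the association alone.
- **A change score would be valid too.** It would, and it would repair the mismatch with the aim. At the implied r = 0.5, however, it has no more power than the post-only analysis, and at 0.3 it has less.
- **Stronger readings.** A reader might infer that baseline spread swamps the exercise response. The plan's figures do not show that: the expected rise equals the baseline SD, and at the implied r = 0.5 baseline accounts for 25% of post-exercise variance. It would take r of about 0.7 to 0.8 or more, which the documents do not give. A reader might also say that a chance association is three times as likely as 5%. That is the upper end, reached with skewed data; with normal data the factor is 13/5 = 2.6.

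**Conclusion.** The point holds in a limited form. The analysis section does not carry out Specific aim 4, makes no use of a baseline measured in everyone, and names no main test among four at 0.05. This should be changed, but it does not undermine the paired comparisons or the sample size.

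The 13% and 14-16% false-positive rates assume that both methods are run at both time points with two-sided tests. The gain from adjustment at r = 0.5 and n = 16 is about 7 percentage points in version A and 13 in version B. It assumes a 0.5 SD slope, normal untransformed data and a lactate measure unrelated to resting FGF21.

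Because r is unknown, the size of the gain is uncertain. Over post-only it grows with r and is nil or slightly negative near r = 0; over the change score it vanishes near r = 0.9. Adjustment is therefore the sound default, not the winner in every case.

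**What to change.** In the Statistical analysis section, name one main association analysis: a linear regression of post-exercise FGF21 on the change in lactate, with pre-exercise FGF21 as covariate, reporting the slope with its 95% CI. Use the log scale for FGF21 if it is skewed; the power figures above were not computed on that scale. Make Spearman supportive and the pre-exercise correlation descriptive, and word Specific aim 4 to match.

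Cost: wording, and one degree of freedom (residual degrees of freedom fall from 14 to 13 at n = 16), which the adjusted power figures already include. No further participants, samples or visits are needed.
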